3.9.3. Vital Signs, Body Weight, and ECG

3.9.3.1. Vital Signs

Descriptive statistics for vital signs and changes from baseline values at each scheduled time point will be presented by treatment group.

Vital sign values will be considered PCS if they meet both the observed-value criteria and the change-from-baseline criteria listed in Table 5. The number and percentage of subjects with PCS post-baseline values will be tabulated by treatment group. The percentages will be calculated relative to the number of subjects with available non-PCS baseline values and at least 1 post-baseline assessment. The numerator will be the total number of subjects with available non-PCS baseline values and at least 1 PCS post-baseline value. A supportive tabular display of subjects with PCS post-baseline values will be provided, including the subject ID number, baseline, and all post-baseline (including non-PCS) values.

All vital signs will be presented in the subject data listing.

Orthostatic hypotension (20/10) is defined as a fall in systolic blood pressure of at least 20 mmHg and a fall in the diastolic blood pressure of at least 10 mmHg upon standing from supine. Orthostatic hypotension (30) is defined as a fall in systolic blood pressure of at least 30 mm Hg upon standing from supine.

Orthostatic tachycardia is defined as a heart rate increase of 30 beats per minute (bpm) or more upon standing from supine, or over 120 bpm upon standing.

The number and percentage of subjects with orthostatic hypotension or orthostatic tachycardia occurring at any post-baseline visit will also be summarized by treatment group for the double-blind period.

Table 5: Criteria for Potentially Clinically Significant (PCS) Blood Pressure or Pulse Rate

Parameter	Criteria
Supine Systolic Blood Pressure	≤90 and decrease ≥20 mm Hg ≥180 and increase ≥20 mm Hg
Supine Diastolic Blood Pressure	≤50 and decrease ≥15 mm Hg ≥105 and increase ≥15 mm Hg
Supine Heart Rate	≤50 and decrease ≥15 bpm ≥120 and increase ≥15 bpm

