### 5.2.2. Olanzapine

Olanzapine has been available in the US since 1996 and was originally approved for the treatment of schizophrenia, but has since been approved for other indications including the treatment of schizophrenia in adolescents and bipolar disorder. The safety and tolerability profile

of olanzapine is well documented, and adverse event labeling is supported by an extensive safety database that includes over 8,500 adult patients ([Eli Lilly and Company 2015](#)). Commonly reported AEs consistent across all or most dosage forms in short-term, placebo controlled trials include somnolence, constipation, dry mouth, accidental injury, weight gain, postural hypotension, dizziness, asthenia, fever and abnormal gait.

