**Table 1: Schedule of Visits and Assessments (Continued)**

Period	Screening	Double-Blind Treatment Period					Follow-Up 
Visit Number	1	2	3	4	5	6	7
Study Day	-10 to -1	1	8	15	22 	29/ET 	43 
Concomitant Medication Review	X	X	X	X	X	X	X
Columbia-Suicide Severity Rating Scale (C-SSRS) 	X	X 	X	X	X	X	X
Abnormal Movement Scales 		X 	X	X	X	X	X
Positive and Negative Syndrome Scale (PANSS) 	X	X 	X	X	X	X	
Modified Overt Aggression Scale 		X	X	X	X 	X 	
Clinical Global Impression – Severity (CGI-S)	X 	X	X	X	X	X	
Clinical Global Impression – Improvement (CGI-I)			X	X	X	X	
Informed Consent for ALK3831-A306						X 	
Emergency treatment card 		X				X	
Admission to Inpatient Unit 	X						
Discharge from Inpatient Unit 				X	X	X	
Study Drug Dispensation 		X	X	X	X		
Study Drug Return and Adherence Review			X	X	X	X	

 Follow-up Visit (V7) is not required for subjects who enroll in ALK3831-A306 A visit window of ±2 days (anchored to Day 1) is allowed Predose Full physical exam at screening; brief physical exam at all subsequent time points.

-  Urine drug screen via dipstick at screening and prior to randomization on Day 1. Drug screen at Visits 5 and 6 applies to outpatient subjects only. Urine drug screen includes opiates, phencyclidine (PCP), amphetamine/methamphetamine, and cocaine.
-  For outpatient subjects only
-  Serology testing includes anti-human immunodeficiency virus (HIV) antibody, hepatitis B surface antigen, and anti-hepatitis C antibody.
-  Subjects must fast (no food or drink except water) for at least 8 hours before lab draws. Lab draws are to be conducted in the morning for all specified visits.
-  One PK sample will be collected at the specified visits to measure plasma levels of olanzapine, samidorphan, and metabolites of interest
-  Vital signs include orthostatic blood pressure and heart rate, respiratory rate, and oral body temperature. Blood pressure, pulse rate, and respiratory rate will be taken after the subject has been supine for 5 minutes and once again after the subject has stood for 2 minutes.

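### SAP 3.9.3.1 leaves some postural falls that pass one of its own limits (systolic 20-29 mmHg alone, diastolic 10 mmHg or more alone) out of its only by-arm count

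*SAP*

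**What the plan says.** SAP 3.9.3.1 (Vital Signs) labels its definitions (20/10) and (30). The first requires "a fall in systolic blood pressure of at least 20 mmHg and a fall in the diastolic blood pressure of at least 10 mmHg", both on standing from supine. For the second: "Orthostatic hypotension (30) is defined as a fall in systolic blood pressure of at least 30 mm Hg upon standing from supine"; it has no diastolic condition.

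The planned output is "The number and percentage of subjects with orthostatic hypotension or orthostatic tachycardia occurring at any post-baseline visit", by treatment group for the double-blind period. The section also states that "All vital signs will be presented in the subject data listing". The blood pressure rows of SAP Table 5 use supine values (for example "Supine Systolic Blood Pressure") and require a change from baseline.

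Protocol Table 1 schedules vital signs at every visit. Its footnote has blood pressure "taken after the subject has been supine for 5 minutes and once again after the subject has stood for 2 minutes". Protocol 5.2.2 includes "postural hypotension" among the commonly reported adverse events of olanzapine.

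**The concern.** The first definition joins its limits with an *and*. The second relaxes the diastolic condition only once the systolic fall reaches 30 mmHg. A diastolic fall alone never counts, however large, and a systolic fall alone does not count between 20 and 29 mmHg.

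Safety and tolerability is the secondary objective, two of the three arms receive olanzapine, and the protocol names postural hypotension as a known effect. The table that turns the supine and standing readings into a rate per arm should therefore let a reader see systolic and diastolic falls separately. As planned it cannot. Elsewhere the SAP is more generous: orthostatic tachycardia, in the same section, uses an *or* rule, and lipids, glucose and QTc have several graded rows.

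**Working it through.** The plan states no orthostatic rate, so there is no figure to reproduce.

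**Step 1: what the rule covers.** Let S and D be the systolic and diastolic falls in mmHg. Taking both definitions together, which is the most generous reading:

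- SAP rule: (S ≥ 20 and D ≥ 10) or S ≥ 30
- Either-limit rule, at the SAP's own 20 and 10: S ≥ 20 or D ≥ 10

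| S | D | (20/10) | (30) | Either limit |
|---|---|---|---|---|
| 20 | 10 | yes | no | yes |
| 30 | 0 | no | yes | yes |
| 28 | 8 | no | no | yes |
| 15 | 25 | no | no | yes |

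Enumerating whole-number pairs (S from -10 to 60, D from -10 to 40), exactly two regions pass a limit without being counted: S of 20-29 with D < 10, and D ≥ 10 with S < 20. No pair that meets the SAP rule fails the either-limit rule.

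**Step 2: does other output close the gap?** Table 5 is supine only, so it cannot register a postural fall. The by-visit summaries cover vital sign values and change from baseline; a supine-to-standing difference is not specified. Listings give no rate. Adverse event tables count what was reported, not what was measured.

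**Step 3: illustrative size for one assessment.** All inputs are assumptions: bivariate normal falls, mean S/D of 0/-3, 4/-1 or 8/1, SD 10/7 or 12/8, correlation 0.3, 0.5 or 0.7. Over these 18 settings the rate is 0.4-8.3% under the SAP rule and 4.5-24.9% under the either-limit rule. The share caught is 7-39%.

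**Step 4: illustrative size per subject, the unit the SAP tabulates.** Further inputs:

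- 130 per arm (SAP section 2).
- Four post-baseline treatment visits (Protocol Table 1, Visits 3-6).
- Assumed: 40% of the variance lies between subjects, SDs are equal in the two arms, and only the means shift.

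One setting in full: mean S/D of 5/-2 on placebo and 10/2 on active, SD 11/8, correlation 0.5. With z = (p1 - p0) / √[p1(1 - p1)/130 + p0(1 - p0)/130]:

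| | Active p1 | Placebo p0 | z | Relative risk |
|---|---|---|---|---|
| SAP rule | 24.4% | 9.5% | 0.149/0.0456 = 3.3 | 2.6 |
| Either limit | 59.5% | 35.3% | 0.242/0.0601 = 4.0 | 1.7 |

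The share caught is 24.4/59.5 = 41% on active and 9.5/35.3 = 27% on placebo.

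Thirteen more settings were run. One is the same shift with SD 13/9 and correlation 0.6. The other twelve step from 0/-3 to 4/-1, or from 4/-1 to 8/1, over the SDs and correlations of Step 3. In all fourteen, z is lower under the SAP rule (1.4-3.3 against 2.2-4.0) and the relative risk is higher (1.7-3.1 against 1.4-1.8). The share caught is 21-52% in 18 of the 22 distinct arm profiles and 9-16% in the other four, which combine low mean falls with weaker correlation. If visits are independent within subjects, it reaches 53% for mean 10/2, SD 13/9, correlation 0.6.

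**The case against.** Every threshold leaves some values uncounted. Neither document supplies a reference definition or an *or* rule, so no benchmark exists against which the count falls short. Requiring both falls, with a separate row for large systolic falls, is coherent and pre-specified, and it is the same in every arm. The readings remain in the listings, and any postural event recorded as an adverse event is tabulated by preferred term whatever the size of the fall. The table carries no test and no decision.

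All of this stands. A reader might go further and infer that the plan understates an olanzapine effect, misses most affected subjects, or biases the comparison with placebo. The documents do not support that. Knowing that postural hypotension is common with olanzapine does not say which pattern of falls defines it, and lower rates in all arms are not bias.

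The loss of sensitivity is not universal either. If the active arm also has larger SDs (placebo mean 5/-2, SD 11/8, correlation 0.5; active mean 10/2, SD 13/9, correlation 0.6), z is practically equal under the two rules. It is 5.87, 5.09 and 4.63 under the SAP rule against 5.96, 5.07 and 4.68, for between-visit correlations of 0, 0.3 and 0.5. The relative risk is then 3.5-3.7 against 1.8.

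What the objection does not answer is narrower: no planned output gives, by arm, the rate of measured falls that pass just one of the SAP's own limits.

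**Conclusion.** The gap is certain, because it follows from the two definitions alone. Its size is not known. The figure of about 20-53% of either-limit subjects caught, with lower values in some settings, rests on assumed means, SDs, correlations and normality. So does the modest loss in z, which also needs a shift in means with equal SDs. These figures show that the omitted patterns need not be rare; they are not estimates for this trial.

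The point is a cheap improvement to a descriptive safety summary. It affects neither the primary analysis nor the type I error, and it does not make the current rows wrong.

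**What to change.** Keep the (20/10) and (30) rows. Add three descriptive rows to the same table, by treatment group, for subjects with any of the following at any post-baseline visit of the double-blind period:

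- systolic fall of at least 20 mmHg from supine to standing;
- diastolic fall of at least 10 mmHg from supine to standing;
- either of these.

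If the sponsor prefers the joint rule alone, one sentence in SAP 3.9.3.1 giving the reason would let a reader judge it.

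The readings are already scheduled, so no visit, procedure or clinical rule changes. The cost is a few table rows and their programming. The added rates will look higher in every arm, placebo included, so a footnote should say that the rows overlap and use single-limit criteria. Specifying the rows before unblinding avoids any suggestion that they were chosen on the results.

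### The pooled orthostatic tachycardia count in SAP 3.9.3.1 depends on resting heart rate as well as on the response to standing, and the planned table cannot separate the two

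*SAP*

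**What the plan says.** SAP 3.9.3.1 (Vital Signs) gives a rule with two limbs joined by *or*: "a heart rate increase of 30 beats per minute (bpm) or more upon standing from supine, or over 120 bpm upon standing". On counting, it says: "The number and percentage of subjects with orthostatic hypotension or orthostatic tachycardia occurring at any post-baseline visit will also be summarized by treatment group". No split by limb is planned, and no baseline condition is attached to this count.

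The neighbouring rules in the same section are built differently:

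- **Orthostatic hypotension.** Both versions depend only on the change between postures, for example "Orthostatic hypotension (30) is defined as a fall in systolic blood pressure of at least 30 mm Hg upon standing from supine".
- **Supine vital signs (Table 5).** "Vital sign values will be considered PCS if they meet both the observed-value criteria and the change-from-baseline criteria listed in Table 5". For high supine heart rate the row reads "≥120 and increase ≥15 bpm". The denominator also excludes an abnormal baseline: "The percentages will be calculated relative to the number of subjects with available non-PCS baseline values and at least 1 post-baseline assessment".

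Protocol 8.3.5 has heart rate measured supine and again after standing, so the rise can be calculated at each visit. Protocol Table 1 schedules vital signs predose on Day 1 and at four later double-blind visits (Days 8, 15, 22 and 29).

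**The concern.** The name and the first limb point to a response to standing. The second limb is a level, not a change. A subject with a fast supine rate can pass 120 bpm with a small rise, no rise or even a fall, and is then counted as having a postural event.

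This is the only by-arm count of orthostatic tachycardia from measured heart rates that the SAP plans. If one arm has a higher resting rate for any reason, such as agitation, drug effect or concomitant medication, its count goes up even when its response to standing is the same as in the other arms. A true postural difference is also harder to see among events that reflect resting rate. Postural response is a relevant safety question here: Protocol 5.2.2 lists postural hypotension among the common adverse events of olanzapine.

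**Working it through.** The documents state no expected rate for this event, so there is no plan figure to reproduce.

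**Step 1. Apply the rule as written.**

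| Supine (bpm) | Standing (bpm) | Rise (bpm) | Limb met | Counted |
|---|---|---|---|---|
| 121 | 121 | 0 | >120 only | yes |
| 125 | 121 | -4 | >120 only | yes |
| 118 | 121 | 3 | >120 only | yes |
| 100 | 121 | 21 | >120 only | yes |
| 70 | 100 | 30 | rise only | yes |
| 70 | 99 | 29 | neither | no |

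A subject at supine 121 at baseline and throughout has no 15 bpm increase and so cannot enter the high supine heart rate row of Table 5. The same subject enters the orthostatic count at any visit where the standing rate is over 120.

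**Step 2. Size under assumed distributions.** All heart-rate inputs are assumptions; only the four visits come from the documents.

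- Supine rate = mean + subject effect (SD 11) + visit effect (SD 7). Total SD = √(121 + 49) = 13.0.
- Rise = mean + subject effect (SD 5) + visit effect (SD 6). Total SD = √(25 + 36) = 7.8.
- Standing rate = supine + rise. A subject is counted if either limb is met at any of the four visits. 400,000 subjects are simulated.

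Hand check for one visit at supine mean 80 and mean rise 10:

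- P(rise ≥30) = P(Z ≥ 20/7.8) ≈ 0.5%.
- P(standing >120) = P(Z > 30/√(170 + 61)) = P(Z > 30/15.2) ≈ 2.4%.

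Over four correlated visits these become 1.9% and 6.8%.

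Results at mean rise 10 bpm:

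| Supine mean | Rise ≥30 | Standing >120 | Either (pooled) | >120 only | >120 only, share of counted |
|---|---|---|---|---|---|
| 70 | 1.9% | 1.4% | 3.0% | 1.2% | 39% |
| 75 | 1.9% | 3.2% | 4.7% | 2.8% | 60% |
| 80 | 1.9% | 6.8% | 8.0% | 6.2% | 77% |
| 85 | 1.9% | 13.0% | 14.0% | 12.1% | 86% |

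The postural limb does not move. Each 5 bpm step in resting rate moves the pooled count by 4.7 - 3.0 = 1.7, 8.0 - 4.7 = 3.3 and 14.0 - 8.0 = 6.0 points. With 130 subjects per arm (SAP 2), 2 to 6 points is 130 × 0.02 = 2.6 to 130 × 0.06 = 7.8 subjects, ignoring dropout.

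**Step 3. Vary the mean rise.** Share of counted subjects who qualify only through >120:

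| Mean rise | Supine 70 | 75 | 80 | 85 |
|---|---|---|---|---|
| 8 | 49% | 70% | 84% | 91% |
| 10 | 39% | 60% | 77% | 86% |
| 15 | 19% | 35% | 52% | 66% |
| 20 | 9% | 18% | 29% | 41% |

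The shift between arms does not need a high share. With more variable rises, at supine means 75/80/85:

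- Rise mean 12, SD 9: pooled 10.2%/13.9%/20.2%, while rise ≥30 stays near 7.4%.
- Rise mean 15, SD 10: pooled 21.9%/26.1%/32.7%, while rise ≥30 stays near 18.6%.

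**Step 4. Who the second limb captures.** At supine 80 and rise 10, 94% of the >120-only subjects had a rise of at least 10 bpm at a qualifying visit, and their mean rise was 18 bpm. About 64% of all counted subjects qualified only by >120 and had a supine rate over 100 at a qualifying visit. Across the grid in step 3, subjects with no rise at every qualifying visit were under 0.4% of those counted.

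**Step 5. Wider grid.** A separate set of 90 scenarios used supine means 70 to 95 (SD 10 to 14) and rises 8 to 20 (SD 7 to 10). The >120-only share ran from 1% to 99% and exceeded half in 41 of 90. The no-rise share ran from 0% to 1.4%.

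**The case against.** The strongest reply is that the SAP states a deliberate two-part rule: a large rise, or a very high rate on standing. Nothing in the documents contradicts it. Counting only the first limb would drop a subject who goes from 98 to 125 bpm (rise 27), in whom posture clearly plays a part. This stands, and it is a reason to show both limbs and not to delete one.

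The SAP also summarises vital signs by arm and visit and lists all values. A resting difference would therefore be visible elsewhere, and the limbs could be separated afterwards from data already held. This too stands, but the reported percentage would remain ambiguous, and a later split would not be pre-specified.

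A reader might go further and infer that most counted events will be resting tachycardia, or will show no rise at all. The documents do not support this. They contain no heart-rate mean, SD or event rate; the share passes half only under some assumptions; and the no-rise group is very small throughout. Nor is high supine rate already covered by Table 5: that row also needs a 15 bpm increase and a non-PCS baseline, so it captures a narrower group.

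**Conclusion.** The concern holds in a limited form. As written, the second limb has no postural condition, unlike the orthostatic hypotension rules, and neither a change-from-baseline condition nor a baseline exclusion, unlike Table 5. The pooled by-arm count therefore mixes resting rate with the response to standing, and nothing else in the SAP repairs that.

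The text alone establishes the mixing; its size depends on the assumed distributions above. How large a part the second limb plays is unknown in advance, since its share varies about tenfold over plausible inputs. The shift of about 2 to 6 points per 5 bpm of resting rate is for a mean rise of 10 bpm.

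This is one descriptive safety row with no hypothesis test. Which heart-rate threshold is clinically right is not judged here.

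**What to change.** In SAP 3.9.3.1, report by arm as separate rows:

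- (a) subjects with a rise of 30 bpm or more from supine to standing;
- (b) subjects with a standing rate over 120 bpm without that rise, not labelled orthostatic on its own;
- (c) optionally, the pooled count, kept beside them if comparability with other tables is wanted.

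State the baseline handling as well: either exclude subjects who already meet the rule at baseline, as Table 5 does for its own criteria, or show them separately. The orthostatic hypotension rows share the same counting sentence and have no stated baseline condition either, so one sentence can cover both.

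The cost is a wording change and one or two extra rows. No new data are needed, because supine and standing rates are already collected predose on Day 1 and at each later visit.

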3.9.3.2. Weight and Body Mass Index

Weight (kg), BMI (kg/m²) and waist circumference (baseline and change from baseline) will be summarized by treatment group. Height (cm) will be measured at the screening visit and this value will be used for the calculation of the BMI. All weight, BMI and waist circumference data will be listed.

Number and percentage of subjects with weight change values considered as PCS occurring at any post-baseline visit will be summarized by treatment group. Criteria for PCS are presented below. The percentages will be calculated relative to the number of subjects in the Safety Population with at least one post-baseline value. A supportive listing will be provided for subjects with PCS values.

Table 6: Criteria for Potentially Clinically Significant (PCS) Changes from Baseline in Body Weight

Parameter	Criteria
Body Weight	Decrease from Baseline $\geq 7\%$ Increase from Baseline $\geq 7\%$

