Subjects completing 4 weeks of treatment with study drug will be eligible to continue in the open-label, long-term safety study (ALK3831-A306) and receive ALKS 3831 for up to 52 weeks. Subjects not continuing in the long term safety study will enter a 2-week safety follow-up period. During this follow-up period subjects may be treated with any antipsychotic medication according to physician recommendations.

Subjects who are inpatient at the end of the 4-week treatment period and are not continuing in the extension study (ALK3831-A306) may continue as inpatients for up to 1 additional week of the 2-week safety follow-up period. These subjects may be discharged from the inpatient unit at any time during this week based on investigator's judgment. For subjects continuing in the safety extension study (ALK3831-A306), details regarding the additional inpatient week will be provided in the ALK3831-A306 protocol.

The total duration of this study is approximately 7.5 weeks, including a 10-day screening period (Days -10 to -1), a 4-week treatment period (Days 1-29), and 1 follow-up visit 2 weeks after EOT (Day 43).

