**Table 1: Schedule of Visits and Assessments**

Period	Screening	Double-Blind Treatment Period					Follow-Up 
Visit Number	1	2	3	4	5	6	7
Study Day	-10 to -1	1	8	15	22 	29/ET 	43 
Informed Consent	X						
Demographics	X						
Medical/ Psychiatric History	X						
Mini International Neuropsychiatric Interview (MINI)	X						
Eligibility Criteria Review	X	X 					
Genotype Sample	X						
Height	X						
Weight and waist circumference (conducted 3 times each visit)	X	X 				X	X
Physical Exam 	X	X 				X	X
Randomization		X					
Urine Drug Screen 	X	X 			X 	X 	
Pregnancy Testing	X	X 					
Serology Testing 	X						
Laboratory Samples  (refer to Table 2 )	X	X 		X		X	
PK Sample 		X 		X		X	
Vital Signs 	X	X 	X	X	X	X	X
12-Lead Electrocardiogram	X	X 	X	X	X	X	X
Adverse Event Monitoring	X	X	X	X	X	X	X

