6.1. Analysis Visit Windows

Scheduled analysis visits are visits at scheduled timepoints as specified in the protocol ([Table 1 Schedule of Visits and Assessments](#)).

Scheduled analysis visits during the study period will be the same as the nominal visits collected in eCRF. There will be one valid value of assessment kept for each scheduled analysis visit in summary/analysis statistics.

Unscheduled visits are visits with data not collected on the scheduled time point. Unscheduled visits will not be used for by-visit summary/analysis statistics unless specified otherwise.

All unscheduled visits will be included as collected in eCRF in listings.

Visit Day is calculated as (visit date) – (date of the first dose of study drug) +1.

Last postbaseline values are defined as the last valid postbaseline values collected for each subject during the double-blind treatment period.

Any post-baseline values are defined as any valid values collected from scheduled visits if applicable.

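### The count of subjects with a 7% or greater weight change has no end date, so it takes in the off-drug Day 43 weight, which is expected only from subjects who do not enter the extension

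*SAP*

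**What the plan says.** **The rule.** SAP 3.9.3.2 says: "Number and percentage of subjects with weight change values considered as PCS occurring at any post-baseline visit will be summarized by treatment group". Table 6 of the SAP sets the potentially clinically significant (PCS) criterion at 7% or more, as an increase or as a decrease. The denominator is every subject in the Safety Population with a post-baseline value. Neither numerator nor denominator carries a period limit.

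**What counts as post-baseline.** SAP 6.1: "Any post-baseline values are defined as any valid values collected from scheduled visits if applicable". The same section ties scheduled visits to the protocol schedule: "Scheduled analysis visits are visits at scheduled timepoints as specified in the protocol".

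**The schedule.** In protocol Table 1, the row "Weight and waist circumference (conducted 3 times each visit" has four marks: Visit 1, Visit 2 (predose), Visit 6 (Day 29/ET) and Visit 7 (Day 43).

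**What happens by Day 43.** Protocol 8.1 places Visit 7 two weeks after end of treatment and adds: "During this follow-up period subjects may be treated with any antipsychotic medication according to physician recommendations". Footnote 1 of Table 1 says: "Follow-up Visit (V7) is not required for subjects who enroll in ALK3831-A306".

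**How the SAP treats comparable summaries.** SAP 6.1 does set a period limit for a neighbouring term: "Last postbaseline values are defined as the last valid postbaseline values collected for each subject during the double-blind treatment period". SAP 3.9.3.1 counts subjects with "orthostatic hypotension or orthostatic tachycardia occurring at any post-baseline visit will also be summarized by treatment group for the double-blind period". SAP 3.9.5 limits the suicidality counts to double-blind treatment. SAP 3.9.1 reports treatment-emergent events for the double-blind period and tabulates follow-up adverse events on their own.

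**The concern.** A 7% count by randomised arm is normally read as weight change on the assigned drug. As written, a subject who stops study drug, receives another antipsychotic and first reaches the threshold at Day 43 is counted under the arm left two weeks earlier. A subject who loses 7% after stopping is counted in the same way.

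The extra measurement is also not spread evenly. Only subjects who complete 4 weeks are eligible for the extension (protocol 8.1), and early terminators are asked to complete safety follow-up (protocol 7.3). The second look therefore falls to early terminators and to completers who do not enter the extension. If dropout or extension uptake differs by arm, so does the number of chances to cross 7%.

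Less weight gain than with olanzapine is part of the product's stated background (protocol 5.1), safety and tolerability is the secondary objective (protocol 6.2), and this count is the SAP's only categorical weight summary. It should mean one thing.

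**Working it through.** **1. Reading the rule**

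| Step | Source | Result |
|---|---|---|
| Which values count | SAP 3.9.3.2 | Any post-baseline visit |
| Meaning of post-baseline | SAP 6.1 | Any valid value from a scheduled visit; no period limit |
| Scheduled post-baseline weights | Protocol Table 1 | Visit 6 (Day 29/ET) and Visit 7 (Day 43) only |
| Drug status at Visit 7 | Protocol 8.1 | Study drug stopped; any antipsychotic allowed |
| Who is expected at Visit 7 | Protocol Table 1, footnote 1; 7.3; 8.1 | Subjects not entering the extension |

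So one of two scheduled post-baseline weights is off study drug, and it enters both numerator and denominator. SAP 7 also admits unscheduled and repeat measurements to the PCS counts, again with no period limit.

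**2. Size for one arm (illustration only)**

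The plan states no weight figure to reproduce. Let p be the share crossing 7% by Day 29/ET, f the share of the arm with a Day 43 weight, and q the chance of a first crossing at Day 43. The documents give none of these. Then

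any-visit rate = p + (1 − p) × f × q.

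Assume p = 5–25%, f = 20–50%, q = 2–10%, with 130 per arm (SAP 2) all in the denominator.

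- Smallest addition: 0.75 × 0.20 × 0.02 = 0.0030, or 0.3 points (0.39 subjects).
- Middle case: 0.85 × 0.30 × 0.05 = 0.0128; 15.0% becomes 16.3% (1.7 subjects).
- Largest addition: 0.95 × 0.50 × 0.10 = 0.0475, or 4.75 points (6.2 subjects).

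Disposition alone can separate two arms. With p = 15% and q = 5% in both, f = 20% gives 15.85% and f = 50% gives 17.1%, a gap of about 1.3 points with no difference in drug effect.

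**3. Direction between arms (illustration only)**

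Assume percent weight change X at Day 29 is normal with SD 3 and mean 0.3 (placebo-like) or 3 (olanzapine-like). Assume the further change D by Day 43 is independent of X and normal with mean d and SD 1.5. Then p = P(X ≥ 7), which is 1.28% (z = 6.7/3 = 2.23) and 9.12% (z = 4/3 = 1.33). The any-visit rate is p + f × P(X < 7 and X + D ≥ 7). By numerical integration:

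| d | f | Placebo-like (on-drug 1.28%) | Olanzapine-like (on-drug 9.12%) | Difference (on-drug 7.84) |
|---|---|---|---|---|
| 0 | 30% | 1.69% | 10.53% | 8.84 |
| 0 | 60% | 2.10% | 11.94% | 9.84 |
| 0.5 | 30% | 1.93% | 11.27% | 9.33 |
| 1.5 | 60% | 4.20% | 17.63% | 13.44 |

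Three things follow.

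- With the same d and f in both arms, the absolute difference widens, while the ratio shrinks (9.12/1.28 = 7.1 on drug; 17.63/4.20 = 4.2 in the last row).
- With unequal d and f it can narrow. Pairing the placebo-like 4.20% (d = 1.5, f = 60%) with the olanzapine-like 10.53% (d = 0, f = 30%) gives 6.33 points, below 7.84.
- Part of the rise is not drift. With d = 0 and f = 30%, the olanzapine-like rate rises by 10.53 − 9.12 = 1.41 points, against 11.27 − 9.12 = 2.15 with d = 0.5. About two thirds of that rise (1.41/2.15 = 66%) is simply a second noisy look at the threshold.

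**The case against.** **The stronger reading.** A reader might infer that counting Day 43 raises the ALKS 3831 and placebo rates and so blurs the contrast with olanzapine. The documents do not support that. They say nothing of weight change after Day 29, of extension uptake by arm, or of how many subjects switch and to what; the antipsychotic provision is permissive. The olanzapine arm has Day 43 weights too, and weight may fall off drug. The illustration shows that the contrast can move either way.

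**The consequence is modest.** This is a descriptive safety count. Weight is not an efficacy endpoint here. SAP 3.1 keeps formal comparisons to ALKS 3831 versus placebo, with olanzapine versus placebo exploratory, so no ALKS 3831 versus olanzapine weight test is planned. All weights are listed, so a careful reader could see at which visit a crossing occurred. This stands and limits the weight of the point.

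**The rule may be narrowed elsewhere.** SAP 3.9.3.2 never names Day 43, SAP 6.1 contains a qualifier about applicability, and the dataset specifications, programming specifications and table shells are separate documents not available here. A filter may sit there, but it would not cure the rule as the SAP states it.

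**It may be deliberate.** An inclusive outlier count is a defensible safety choice. But the SAP gives no such reason, and it limits the orthostatic and suicidality counts and separates follow-up adverse events.

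**Conclusion.** The concern holds as a defect of definition. On the SAP's own terms, the 7% count includes a weight taken two weeks after end of treatment, possibly on another antipsychotic, in a subset fixed by what happened after randomisation. The percentage then combines on-drug change, off-drug change and an extra look at the threshold. Increases and decreases are both affected.

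The size is not determinable from the documents. The 0.3 to 4.75 points per arm rests wholly on the assumed p, f and q, and the two-arm table on assumed means and SDs. No direction should be claimed for the between-arm contrast. The primary and key secondary analyses are untouched. The point is worth fixing because the change is small and brings this count into line with the SAP's rules for similar summaries.

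**What to change.** - In SAP 3.9.3.2, limit both numerator and denominator of the PCS weight count to the double-blind period, from first dose to Visit 6/ET.
- Tabulate the Day 43 weight separately, with subjects who have a Visit 7 as the denominator, following the SAP's separate table for follow-up adverse events.
- For consistency with the orthostatic rule, add the double-blind limit to the PCS counts for vital signs (3.9.3.1) and QTc (3.9.3.3). Table 1 schedules both at Visit 7. The effect is smaller there, because each has four on-treatment assessments (Visits 3 to 6). Table 1 schedules no laboratory samples at Visit 7, so the laboratory counts do not need this change.
- In the same edit, reconcile SAP 6.1 (scheduled visits) with SAP 7 (unscheduled values included in PCS counts), and state that the period limit applies to both.

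The cost is a few words and a date filter, with no change to trial conduct. Follow-up values stay in their own table and in the listings. A subject with a Visit 7 weight but no weight up to Visit 6/ET leaves the main denominator; report how many there are by arm.
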